	Appendix C (Definitions of Invasive Fungal Disease
	[IFD]).

 - 10.2. Treatment Compliance32
 - 10.3. Adverse Events.....32
 - 10.4. Laboratory Evaluations.....34
 - 10.5. Vital Signs34
 - 10.6. 12-Lead ECG.....34
 - 10.7. Physical Examination34
- 11. Interim Analyses35
- 12. Changes from Analysis Planned in Protocol.....36
- 13. Programming Considerations.....37
 - 13.1. General Considerations.....37
 - 13.2. Table, Listing, and Figure Format37
 - 13.2.1. General.....37
 - 13.2.2. Headers37
 - 13.2.3. Display Titles.....38
 - 13.2.4. Column Headers38
 - 13.2.5. Body of the Data Display.....38
 - 13.2.6. Footnotes40
- 14. Appendices.....42
 - 14.1. Treatment Outcome42
 - 14.2. PopPK analysis plan43

1. Glossary of Abbreviations

Abbreviation	Description
ACM	All-Cause Mortality
AE	Adverse Event
ATC	Anatomical Therapeutic Chemical
AUC	Area Under the Concentration-Time Curve
AUC _{0-inf}	Area under the concentration-time curve extrapolated to infinity
AUC _{0-last}	Area under the curve from the time of dosing to the last measurable concentration
BMI	Body Mass index
CI	Confidence Interval
CL/F	Apparent clearance
C _{max}	Maximum Concentration
CT	Computed Tomography
DRC	Data Review Committee
ECG	Electrocardiogram
EoT	End of Treatment
FU	Follow-Up
GMI	Galactomannan Index
λ_z	Terminal elimination phase rate constant
HCT	Hematopoietic Cell Transplantation
HM	Hematological Malignancy
ICU	Intensive Care Unit
IPA	Invasive Pulmonary Aspergillosis
ITT	Intent-to-Treat
IV	Intravenous
Max	Maximum
MedDRA	Medical Dictionary for Regulatory Activities
Min	Minimum
MITT	Modified Intent-to-Treat
NG	Nasogastric
PEG	Percutaneous Endoscopic Gastrostomy

Statistical Analysis PlanSponsor: Scynexis, Inc.; Protocol No.: SCY-078-206

Abbreviation	Description
PK	Pharmacokinetics
PP	Per Protocol
PT	Preferred Term
QTc	Corrected QT Interval
SAE	Serious Adverse Event
SAP	Statistical Analysis Plan
SD	Standard Deviation
SOC	System Organ Class
SOP	Standard Operating Procedure
TEAE	Treatment Emergent Adverse Event
T _{max}	The first time to maximum observed concentration sampled during a dosing interval
TFL	Table, Figure and Listing
WHODD	World Health Organization Drug Dictionary

2. Purpose

The purpose of this statistical analysis plan (SAP) is to ensure that the data listings, summary tables and figures which will be produced, and the statistical methodologies that will be used, are complete and appropriate to allow valid conclusions regarding the study objectives.

2.1. Responsibilities

████████████████████ will perform the statistical analyses and are responsible for the production and quality control of all SDTM datasets, ADaM datasets, tables, figures and listings.

2.2. Timings of Analyses

The primary analysis of safety, efficacy and pharmacokinetics is planned after all subjects complete the final study visit or terminate early from the study.

3. Study Objectives

3.1. Primary Objective

To evaluate the safety and tolerability of the coadministration of ibrexafungerp and voriconazole compared with coadministration of ibrexafungerp placebo and voriconazole in the treatment of invasive pulmonary aspergillosis (IPA).

3.2. Secondary Objectives

- To evaluate the efficacy of the coadministration of ibrexafungerp and voriconazole compared with that of ibrexafungerp placebo and voriconazole in the treatment of IPA.
 - based on Global Response
 - as determined by the DRC
 - as determined by the Principal Investigator
 - based on all-cause mortality (ACM)
 - based on serum galactomannan index (GMI) decrease
 - based on clinical response, mycological response and radiological response
 - as determined by the DRC
 - as determined by the Principal Investigator
- To evaluate the pharmacokinetics (PK) of ibrexafungerp and voriconazole.

3.3. Exploratory Objectives

The exploratory objectives will be evaluated as data allow and include:

- To evaluate the efficacy of the coadministration of ibrexafungerp and voriconazole compared with coadministration of ibrexafungerp placebo and voriconazole
 - based on other biomarkers of fungal infection (i.e., serum levels of β -D-glucan and plasma *Aspergillus* PCR)
 - based on change in the performance indicator (i.e., Karnofsky score)
 - based on the rate of recurrence of IPA at Week 6 after end of treatment (EoT) as determined by the DRC
 - based on the need for additional systemic antifungal treatment (other than secondary prophylaxis) until Week 6 after EoT
- To evaluate the relationship between selected endpoints to ACM at Days 42 and 84.
- To evaluate healthcare resources utilization for the patients receiving the coadministration of ibrexafungerp and voriconazole compared with coadministration of ibrexafungerp placebo and voriconazole based on overall hospital stay and intensive care unit stay.
- To assess the effect of the coadministration of ibrexafungerp and voriconazole compared with coadministration of ibrexafungerp placebo and voriconazole on on-schedule administration of planned therapies for the underlying condition.

3.4. Brief Description

This is a multicenter, randomized, double-blind, two-arm study to evaluate the safety, tolerability, efficacy and PK of the coadministration of ibrexafungerp plus voriconazole compared to coadministration of ibrexafungerp placebo plus voriconazole in male and female subjects 18 years of age and older with probable or proven IPA.

The study will be conducted at approximately 30 sites globally (revised to 8 number of sites with subjects randomized). Approximately 90 subjects will be screened to randomize a total of approximately 60 subjects (revised

to approximately 22 subjects randomized , 11 subjects per group) into one of the two treatment groups of the study (ibrexafungerp plus voriconazole or ibrexafungerp placebo plus voriconazole).

Subjects will receive study treatment for the entire duration of the antifungal therapy (i.e., for a recommended minimum of 6 weeks and a maximum of 13 weeks).

The study will consist of a Screening Period (Days -4 to -1) to assess subject eligibility; a Baseline visit (also considered Treatment Day 1) to confirm subject eligibility and begin study treatment; additional scheduled treatment visits (Treatment Days 3, 7, 10, 14 and treatment visits every 14 days thereafter until the EoT) to perform safety, tolerability, efficacy and PK assessments, an EoT visit to assess efficacy outcomes, a Follow-up (FU) visit 6 weeks after EoT (6-Week FU) to assess recurrence and safety, and 2 survival visits/contacts to determine survival status and treatment outcome. The Screening Period and Baseline visit may be combined for certain subjects. Unscheduled visits may also be conducted as needed.

3.5. Subject Selection

The target population is Male or female subjects 18 years of age and older with a probable or proven IPA.

3.5.1. Inclusion Criteria

Subjects must fulfill all of the following key criteria to be eligible for study admission:

1. Subject is a male or female adult ≥ 18 years of age on the day the study informed consent form (ICF) is signed.
2. Subject has a probable or proven IPA based on the protocol-specified criteria (Section 22.3) that requires antifungal treatment.
Note: Subjects with possible IPA may enter the Screening Phase of the study but will only be randomized after meeting criteria for probable or proven IPA.
3. Subject has one of the following:
 - a. a diagnosis of a hematological malignancy or a myelodysplastic syndrome or aplastic anemia or has undergone hematopoietic cell transplantation, **OR**
 - b. who either recently resolved or ongoing neutropenia (neutropenia defined as absolute neutrophil count $< 0.5 \times 10^9/L$ [$< 500/mm^3$] for > 10 days), temporally related to the onset of fungal disease **OR**
 - c. who received treatment with other recognized T-cell immunosuppressants (such as cyclosporine, tacrolimus, monoclonal antibodies or nucleoside analogs) during the past 90 days including solid organ transplant patients. **OR**
 - d. with inherited severe immunodeficiency (e.g. chronic granulomatous disease, severe combined immunodeficiency).
4. Subject has not received more than 4 days (96 hours) of prior mold-active antifungal therapy for the treatment of the IPA episode in the 7 days preceding enrollment into the study (Baseline/Treatment Day 1). However, subjects who have received more than 4 days but less than 7 days of prior mold-active antifungal therapy for the treatment of the IPA episode in the 7 days preceding enrollment into the study may be enrolled but will require approval from the study medical monitor, who will evaluate each subject on a case-by-case basis.
5. For subjects who are receiving antifungal prophylaxis the IPA episode would, in the investigator's judgement, be adequately treated with voriconazole.

3.5.2. Exclusion Criteria

A subject will be excluded from participation in the study if he or she meets any of the following key exclusion criteria:

1. Subject has a fungal disease with central nervous system involvement suspected at Screening.
2. Subject is receiving, has received or anticipates to be receiving concomitant medications that are listed in the prohibited medication list (Appendix A in full protocol) within the specified washout periods.
3. Subject has a Karnofsky score <20.
4. Subject is expected to die from a non-infectious cause within 30 days from the day the study ICF is signed.
5. Subject is under mechanical ventilation.
6. Subject has abnormal liver test parameters: AST or ALT ≥ 5 x ULN and/or total bilirubin >2.5 x ULN.

Note: Subjects with unconjugated hyperbilirubinemia (< 7 mg/dL) with a diagnosis of Gilbert's disease **are not excluded**.

3.6. Determination of Sample Size

This is an exploratory study with safety as the primary objective. As a result, no formal sample size calculations are defined and the data from this study will provide safety data for ibrexafungerp in subjects with a preliminary view of efficacy data which can be used to design future studies.

3.7. Treatment Assignment & Blinding

This is a double-blind study. All site and sponsor personnel will be blinded to treatment assignment. Subject randomization will be performed using an Interactive Web Response System (IWRS).

Approximately 20 eligible subjects (10 subjects per treatment arm) will be randomized in a 1:1 ratio to one of the two study treatment arms: voriconazole and ibrexafungerp or voriconazole and ibrexafungerp placebo. For the purpose of maintaining treatment blinding, all randomized subjects will receive ibrexafungerp or ibrexafungerp matching placebo. Subjects will be randomized at Baseline, after all baseline evaluations have been completed. Only one randomization number and study treatment arm will be assigned to each eligible subject.

Eligible subjects will be stratified to one of these groups at randomization:

- Hematological malignancies and /or hematopoietic cell transplantation recipients
- Solid organ transplant recipients
- Other immunocompromising conditions

The study team will be unblinded at the end of the study, following database lock.

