8.1. Key Efficacy Endpoint and Analysis

The key efficacy endpoint is the assessment of Global Response as determined by the DRC.

The DRC will assess the Global Response at Day 42, Day 84 and EoT.

Analysis of Global Response by the DRC will be for the ITT Population.

Global Response will be summarized at each visit.

In addition, the percentage of subjects with a Global Response, defined as either a complete or partial response at EoT, Day 42 and Day 84 will also be summarized. Subjects with missing data at EoT, Day 42 and Day 84 will be considered as indeterminate response at the corresponding visit. The response rate will be calculated for each treatment group as the number of successes divided by the total number of patients (success + failure + indeterminate).

The difference in response rates between treatments will be presented along with a 95% confidence interval (CI) calculated using the wmethod of Clopper-Pearson.

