8.2.3. All-Cause Mortality

All-cause mortality is defined as all deaths following the first dose of study drug, regardless of attribution. The total number of deaths by Day 42 and Day 84 and relationship to the fungal infection will be summarized. The difference in mortality rates between treatments will be presented along with a 95% CI calculated using the method of Clopper-Pearson.

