10.7. Physical Examination

A general physical examination is done at Screening, Day 1, Day 14, Day 28, Day 42, Day 56, Day 70, Day 84, EoT and at Follow-Up.

Physical examination results will be summarized, by treatment, for the Safety Population.

11. Interim Analyses

The protocol planned for the performance of an interim analysis. However, there is no interim analysis since the study was stopped after enrolment of 22 subjects, due to patient recruitment challenges..

12. Changes from Analysis Planned in Protocol

There are currently no deviations from the analyses planned in the protocol. Enrollment into the study was stopped after 22 subjects were randomized because of the subject recruitment challenges and feasibility to enrol the planned sample size of 60 subjects.

13. Programming Considerations

All tables, figures, listings (TFLs), and statistical analyses will be generated using SAS for Windows, Release 9.4 or higher (SAS Institute Inc., Cary, NC, USA). Computer-generated table, listing and figure output will adhere to the following specifications.

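### Randomisation is stratified by underlying condition, but no planned treatment difference uses the strata; prespecify a stratified sensitivity estimate beside the crude one (minor)

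*SAP*

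**What the plan says.** SAP 3.7 states "Eligible subjects will be stratified to one of these groups at randomization" and lists three groups: hematological malignancy and/or hematopoietic cell transplantation (HM/HCT), solid organ transplant, and other immunocompromising conditions. Protocol 11.2 gives the same list. Subjects "will be randomized in a 1:1 ratio to one of the two study treatment arms".

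The planned comparisons carry no stratum term or weight:

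- Global Response by the DRC (SAP 8.1): "The difference in response rates between treatments will be presented along with a 95% confidence interval (CI) calculated using the wmethod of Clopper-Pearson". SAP 8.2.1, 8.2.7 and 8.2.8 refer back to this method.
- Mortality (SAP 8.2.3): "The difference in mortality rates between treatments will be presented along with a 95% CI".
- GMI targets (8.2.5), beta-D-glucan targets (8.2.10) and PCR conversion (8.2.11): the same form.

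Overall survival (8.2.2) is Kaplan-Meier by arm with no between-arm estimate. The strata are used once, in the demography summary (7.2), and no reason is given for leaving them out elsewhere.

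Protocol 19.0 foresees subgroups by underlying condition if numbers allow, and Protocol 19.7.2 mentions optional matching of patients across arms. The SAP takes up neither. SAP 3.4 revises the size "to approximately 22 subjects randomized , 11 subjects per group", and SAP Section 12 says "Enrollment into the study was stopped after 22 subjects were randomized". SAP 3.7 still gives about 20; I use 22.

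**The concern.** An analysis normally respects the factor used to allocate treatment. If it does not, two things can follow. In a large trial with a prognostic factor, the unstratified interval is somewhat too wide. In a very small trial, strata end part-filled, the arms can differ in case mix, and the crude difference in that dataset carries the discrepancy.

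The second effect is the relevant one here. Protocol 19.1 describes the main goal as obtaining preliminary effect sizes for later studies, so the point estimate itself will be used. Protocol 8.1 notes poor outcomes in stem cell transplant recipients in particular, and these fall in the first stratum. If adjustment is considered only after case mix by arm is known, the choice becomes data-driven.

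**Working it through.** There is no plan figure to reproduce: the SAP says "no formal sample size calculations are defined", and states no power, alpha or effect size.

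**Inputs from the documents.** N = 22, about 11 per arm, 1:1 allocation, three strata.

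**Assumptions (not in the documents).** Permuted blocks of 2 or 4; stratum shares 50/20/30, 70/10/20 or 85/5/10%; response 45/60/65% or 35/70/70% in the order HM/HCT, solid organ transplant, other; no treatment effect. 6,000 simulated trials per scenario.

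**1. Size of a visible imbalance.** If one arm of 11 has two more HM/HCT subjects than the other, and the rest of the arm responds 25 to 35 points better:

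shift = (2/11) × rate gap = 0.182 × 0.25 = 4.5 points, up to 0.182 × 0.35 = 6.4 points.

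**2. How often that happens.** With blocks of 4, a gap of two requires the last HM/HCT block to stop at two subjects (about 1 in 4) with both in the same arm (1 in 3): 1/4 × 1/3 = 1/12, about 8%. Two is also the largest gap possible. With blocks of 2 the largest gap is one, so it never happens.

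**3. What stratified allocation already removes (shares 70/10/20).**

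| Allocation | Mean absolute imbalance in HM/HCT share | 95th percentile of carry-over, 45/60/65% | 95th percentile of carry-over, 35/70/70% |
|---|---|---|---|
| Unstratified | 15 points | 7.3 points | 12.7 points |
| Stratified, blocks of 4 | 7 points | 3.2 points | 6.4 points |
| Stratified, blocks of 2 | 5 points | 2.2 points | 4.7 points |

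Carry-over is the part of the crude difference due only to unequal stratum mix. Over all assumed shares with stratified allocation, its 95th percentile is 1.8 to 6.4 points at N = 22 and 0.7 to 2.5 points at N = 60.

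**4. Bias.** With stratified allocation the mean error of both the crude and the stratified difference was within 0.7 points of zero in every scenario, which is simulation noise.

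**5. Precision at N = 22 (blocks of 4, shares 70/10/20).** With all three strata, the SD of the crude versus the Mantel-Haenszel difference was 0.213 versus 0.217 (45/60/65%) and 0.202 versus 0.204 (35/70/70%). With two collapsed strata the SDs differ by at most about 0.002 in either direction.

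**6. Interval width.** At N = 60 (35/70/70%, blocks of 4) the true SD is 0.121 against an unstratified SE of 0.127; 0.127/0.121 = 1.05, so the crude interval is about 5% too wide. At N = 22 the figures are 0.202 and 0.203, so there is no such effect.

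**7. Scale.** An unstratified score interval for 7/11 versus 5/11 runs from −23 to +54 points, about 77 points wide.

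**8. Does the sensitivity estimate add anything?** The collapsed-strata and crude differences were about 4 to 10 points apart at the 95th percentile. Part of that gap is case mix and part is the noise of reweighting small cells.

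**The case against.** The case for leaving the plan alone is substantial. Stratified allocation is itself the protection against imbalance in this factor. The study is exploratory, safety is its primary objective, and no efficacy test is planned. The strata are tabulated by arm, so a reader can see any imbalance. Stratifying cannot repair imbalance in other factors such as neutropenia. With an assumed 85/5/10 mix, even the combined non-HM/HCT stratum is missing from one arm in 16% (blocks of 2) to 22% (blocks of 4) of simulated trials, and Mantel-Haenszel weighting then gives those subjects no weight. All of this stands. It rules out making the stratified estimate primary, but it does not explain the SAP's silence.

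A reader might infer three stronger things that the documents do not support:

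- *The crude difference is biased, or imbalance generally stays in it.* It is unbiased over repeated stratified allocation, and 4.5 to 6.4 points is a tail outcome.
- *The interval is about 9% too wide.* That figure, √(0.25/0.21) = 1.09, needs a larger sample and strata responding at 30% and 70%. It does not apply to 22 subjects.
- *The factor was chosen because it predicts outcome.* No reason is stated. The revision history ties the current groups to the broadened population, and no outcome rates by these three strata are given.

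**Conclusion.** The mismatch is real: allocation uses three strata, no planned treatment difference does, and the SAP gives no justification. The consequence is small. The crude estimate is unbiased, and stratifying at 22 subjects gains no precision on average. What remains is residual case-mix imbalance in the one dataset observed, typically 0 to a few points and about 6 points in the tail, against an interval about 77 points wide. These sizes rest on assumed block sizes, stratum shares and stratum response rates, none of which the documents give. No conclusion is likely to change. Severity is minor, and the remedy is a prespecified sensitivity analysis, not a new main analysis.

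**What to change.** In SAP 8.1, 8.2.1, 8.2.3, 8.2.5, 8.2.7, 8.2.8, 8.2.10 and 8.2.11:

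1. Report the crude difference with a Miettinen-Nurminen 95% CI. Protocol 19.7.2 already names this method for Global Response. The Clopper-Pearson method now named is for a single proportion; that is a separate defect in the same sentences, so both can be corrected in one edit.
2. Beside it, as a sensitivity analysis, give the Mantel-Haenszel-weighted difference with a stratified Miettinen-Nurminen 95% CI. Use two strata: HM/HCT versus solid organ transplant plus other conditions.
3. If a collapsed stratum has no subject in one arm for a given endpoint and visit, report the crude result only and say so. This may occur more often for endpoints limited to subjects positive at baseline, such as PCR conversion.
4. Fix these rules before database lock and unblinding (SAP 3.7), and record the addition in SAP Section 12.

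The cost is slight extra programming and a second estimate per endpoint, with little or no precision gain at this size. No new data are needed. The minimum alternative is one sentence in the SAP explaining why the stratification factor is not used.

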3.8. Study Procedures and Flowchart

Detailed schedules of all study visits and procedures are presented in the Schedules of Visits and Procedures (Table 1 and Table 2).

Table 1 Schedule of Treatment Visits and Procedures (Study SCY-078-206)

Visit	Screening Period	Baseline(Treatment Day 1)	Treatment Day 3	Treatment Day 5	Treatment Day 7	Treatment Day 10	Treatment Day 14	Every 14 days during treatment ^a	EoT ^b	6-Week FU (6 weeks after EoT)	Unscheduled Visits
Days (allowable window)	Day -4 to Day -1 ^c	0	+1	+1	+1	+1	+1	± 2 days	± 1 day	± 2 days	
Procedure											
Informed Consent	X										
Inclusion/Exclusion Criteria	X	X									
Subject Enrollment and ID Assignment		X									
Randomization		X									
Medical History and Demographics	X										
General Physical exam, including Visual Function Assessment ^d	X	X						X (VFA only, TD28)	X	X	
Vital Signs	X	X							X		If applic.
12-Lead ECG	X	X				X ^e			X		If applic.
Pregnancy Test ^f	X	X							X		
Karnofsky Score	X	X					X	X	X		
Targeted Physical Exam	X	X	X	X	X		X	X	X	X	

Statistical Analysis Plan

Sponsor: Scynexis, Inc.; Protocol No.: SCY-078-206

Visit	Screening Period	Baseline(Treatment Day 1)	Treatment Day 3	Treatment Day 5	Treatment Day 7	Treatment Day 10	Treatment Day 14	Every 14 days during treatment ^a	EoT ^b	6-Week FU (6 weeks after EoT)	Unscheduled Visits
Days (allowable window)	Day -4 to Day -1 ^c	0	+ 1	+1	+1	+1	+1	± 2 days	± 1 day	± 2 days	
Procedure											
including Clinical Evaluation of Signs and Symptoms of Infection											
Chest CT scan		X ^e	If applic.	If applic.	If applic.	If applic.	If applic.	If applic.	X ^h	If applic.	If applic.
Other Imaging		X ⁱ	If applic.	If applic.	If applic.	If applic.	If applic.	If applic.	If applic.	If applic.	If applic.
All Mycological Testing ^j including BAL GMI ^l (other than serum GMI, serum β -D Glucan, and plasma Aspergillus PCR)	X ^k	If applic.	If applic.	If applic.	If applic.	If applic.	If applic.	If applic.	If applic.	If applic.	If applic.
Serum GMI	X ^l	X ^m	X	X	X	X	X	X	X	X	X
Serum β -D Glucan and plasma Aspergillus PCR	X	X	X	X	X	X	X	X	X	X	If applic.
Safety Laboratory Assessments ⁿ	X	X			X		X	If applic. ^o	X	X	If applic.
Voriconazole TDM ^p	If applic.	If applic.	If applic.	If applic.	If applic.	If applic.	If applic.	If applic.	If applic.	If applic.	If applic.
Voriconazole level determination ^q		X	X		X	If applic. ^r	X	If applic. ^r			If applic.

This document is confidential.

Statistical Analysis Plan

Sponsor: Scynexis, Inc.; Protocol No.: SCY-078-206

Visit	Screening Period	Baseline(Treatment Day 1)	Treatment Day 3	Treatment Day 5	Treatment Day 7	Treatment Day 10	Treatment Day 14	Every 14 days during treatment ^a	EoT ^b	6-Week FU (6 weeks after EoT)	Unscheduled Visits
Days (allowable window)	Day -4 to Day -1 ^c	0	+1	+1	+1	+1	+1	± 2 days	± 1 day	± 2 days	
Procedure											
ibrexafungerp Plasma PK ^s		X	X		X		X				
Assessment of treatment outcome									X	X	
Assessment of Recurrence										X	
Study Drug Dispensing		X						X			
Study Drug Dosing ^t		X-----X									
Study Drug Collection and Compliance Evaluation		X-----X									
Subject Diary Dispensing, Collection and Review ^u	X							X	X		
Prior and Concomitant Medication Review	X	X	X	X	X	X	X	X	X	X	X
Adverse Event Monitoring		X	X	X	X	X	X	X	X	X	X

Abbreviations: AE=adverse event; applic.= applicable; BAL = bronchoalveolar lavage; BID = twice daily; ECG=electrocardiogram; eCRF = electronic case report form; EoT=end of

This document is confidential.

Statistical Analysis Plan

Sponsor: Scynexis, Inc.; Protocol No.: SCY-078-206

Visit	Screening Period	Baseline(Treatment Day 1)	Treatment Day 3	Treatment Day 5	Treatment Day 7	Treatment Day 10	Treatment Day 14	Every 14 days during treatment ^a	EoT ^b	6-Week FU (6 weeks after EoT)	Unscheduled Visits
Days (allowable window)	Day -4 to Day -1 ^c	0	+ 1	+1	+1	+1	+1	± 2 days	± 1 day	± 2 days	
Procedure											

treatment; GM = galactomannan; PK = pharmacokinetic(s), QD = once daily; TD = Treatment Day; TDM = therapeutic drug monitoring; VFA = visual function assessment.

- a. Antifungal treatment duration will be for a recommended minimum of 6 weeks and a maximum of 13 weeks.
- b. All EoT procedures should be performed for subjects who discontinue from study treatment before the EoT visit.
- c. The Screening Period and Baseline/Treatment Day 1 visits may be combined.
- d. An overall assessment and questions to investigate visual acuity, visual field and color perception should be conducted by the Principal Investigator or designee during Screening or at Baseline and again at approximately Treatment Day 28 (if voriconazole treatment continues beyond 28 days). An ophthalmologist exam is recommended if there are clinically significant visual function abnormalities identified during the general physical exams at or after Baseline. An ophthalmologist exam is not required for the enrollment of patients into the study but should be conducted as early as possible, if clinically significant visual function abnormalities are identified. Additional evaluations of visual function may be conducted as needed, at the investigator’s discretion. Any visual disturbance identified should be documented either as part of the subject’s medical history and/or as an AE, accordingly.
- e. A 12-lead ECG will also be performed once between Days 7 and 21.
- f. Pregnancy test should be done, locally, once a month, while subject is on study treatment.
- g. A chest CT scan obtained within 5 days prior to enrollment must be available at Baseline (Treatment Day 1).
- h. Follow-up chest CT scans will be performed to evaluate response to treatment, ideally within 3 days prior to or after EoT.
- i. If images other than the chest CT scan are available at Baseline (Treatment Day 1) to support the diagnosis of IPA, subsequent comparative imaging studies will be collected, if available, to evaluate response.
- j. Mycological testing other than serum GMI, serum β-D glucan and plasma *Aspergillus* PCR tests will include fungal cultures (e.g. BAL culture, culture from biopsy), histopathological or cytopathological analysis of relevant tissues or samples (e.g., lung biopsy sample, BAL fluid.), and other tests (BAL GMI).
- k. These procedures will be repeated only if clinically indicated.
- l. At Screening, at least one positive serum or BAL sample collected within 96 hours before enrollment must be available for all subjects. For subjects with a possible IPA, serum or BAL samples will be collected daily for a maximum Screening Period of 4 days (Days -4 to -1) until at least one positive GMI result (≥ 0.5 for serum and ≥ 1 for BAL) is reported. If a positive serum or BAL GMI test is reported after 4 days but no more than 7 days of mold-active antifungal treatment, the case will be discussed with the medical monitor to evaluate eligibility. If GMI results during the Screening period are negative, the subject will not be randomized and will be discontinued from the study.
- m. Samples for serum GMI assessments will be obtained within 2 hours before first dose of randomized treatment.
- n. Clinical safety laboratory assessments by the central laboratory will include hematology, blood chemistry and urinalysis. Additional laboratory tests should be collected and analyzed by the local laboratory, as needed, to make real-time medical decisions. Specifically, in line with voriconazole label recommendations, serum transaminase levels, bilirubin levels, serum electrolytes (potassium, magnesium and calcium) and amylase and lipase should be monitored at initiation of voriconazole therapy (Day 1) and then

Statistical Analysis Plan

Sponsor: Scynexis, Inc.; Protocol No.: SCY-078-206

Visit	Screening Period	Baseline(Treatment Day 1)	Treatment Day 3	Treatment Day 5	Treatment Day 7	Treatment Day 10	Treatment Day 14	Every 14 days during treatment ^a	EoT ^b	6-Week FU (6 weeks after EoT)	Unscheduled Visits
Days (allowable window)	Day -4 to Day -1 ^c	0	+ 1	+1	+1	+1	+1	± 2 days	± 1 day	± 2 days	
Procedure											

weekly during the first month of treatment (Day 7, Day 14 and Day 21, Day 28). Monitoring frequency of these laboratory parameters may be reduced to monthly intervals during continued use of voriconazole if no clinically significant changes are noted.

- o. If the subject is receiving study drug by Day 42 (i.e., EOT has not occurred), a safety lab assessment should be conducted on Day 42 or on Day 56.
- p. Voriconazole TDM will be conducted as per local standard practice and samples will be processed locally. All results available from locally conducted tests of voriconazole plasma concentrations, including those prior to Randomization, will be documented in the eCRF.
- q. Blood samples for voriconazole level determination will be performed for all study subjects at a central laboratory. For the first 20 randomized subjects, blood PK samples will be collected predose on Treatment Days 1, 3, 7 and 14, approximately within 1 hour before dosing and at 2-4 hours and 6-8 hours after dosing on Treatment Days 1, 7 and 14. The PK data from the first 20 subjects will be assessed in an interim PK analysis. For subjects subsequently randomized, blood PK samples will be collected predose on Treatment Days 1, 3, 7 and 14, approximately within 1 hour before dosing, and on Treatment Days 1, 7 and 14 at 4-8 hours after dosing. The time of dosing and sample collection must be recorded in the eCRF.
- r. Blood samples for voriconazole level determination to be collected as needed (e.g., within 7 days after making any dose adjustment or evidence of toxicity) and sent to the central lab.
- s. Samples for ibrexafungerp PK will be collected predose on Treatment Days 1, 3, 7 and 14, approximately within 1 hour before dosing, and at 2-4 hours and 6-8 hours after dosing on Treatment Days 1, 7 and 14.. The time of dosing and sample collection must be recorded in the eCRF and on the subject’s medical record.
- t. All randomized subjects will receive either ibrexafungerp + voriconazole or ibrexafungerp placebo + voriconazole.
- u. For non-hospitalized patients only.

Table 2 Schedule of Treatment Visits and Procedures for Days 42 and 84 (Study SCY-078-206)

PROCEDURE	Visit/contact	Visit/contact
Visit	Survival	Survival
	Day 42	Day 84
Days (allowable window)	± 2	± 4
Assessment of treatment outcome	X	X
Subject Status (alive/ deceased)	X	X
Karnofsky Score	X	X

4. Endpoints

